#### **13.1.4. Suspected Unexpected Serious Adverse Reactions**

Suspected unexpected serious adverse reactions (SUSARs) are AEs that are believed to be related to the trial medication and are both unexpected (i.e., the nature or severity is not expected from the information provided in the Investigator Brochure) and serious.

#### **13.1.5. Expected Adverse Events**

Perceived deterioration of IIH necessitating attendance or admission to hospital will not be reported as an SAE, but these events will be reported and recorded at follow-up. Non-protocol LPs will be reported at follow-up.

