#### **13.1.3. Serious Adverse Events or Serious Adverse Drug Reactions**

An SAE is any untoward medical occurrence that at any dose:

- Results in death
- Is life-threatening
- Requires inpatient hospitalization or prolongation of existing hospitalization
- Results in persistent or significant disability/incapacity

Study Number: INVEX-CLIN-IIH-301 Protocol	Compound No.: Presendin
	Version: 5.0 for EU countries dated 08Dec2022

- Is a congenital anomaly/birth defect

Medical and scientific judgement should be exercised in deciding whether reporting is appropriate in other situations, such as important medical events that may not reach the above definition but may jeopardise the patient or may require medical or surgical intervention to prevent one of the other outcomes listed in the above definition. These should also be considered serious. Examples of such events are invasive or malignant cancers, intensive treatment in an accident and emergency department or at home for allergic bronchospasm, blood dyscrasias or convulsions that do not result in hospitalisation, or development of drug dependency or drug abuse.

Deterioration of IIH necessitating CSF shunting or optic nerve sheath fenestration or dural venous sinus stenting will be recorded as an SAE and reported.

Deterioration of IIH necessitating hospital admission will be recorded as an SAE and reported.

Pre-defined exclusions:

- Hospitalisation for unrelated elective procedures
- Post LP headache

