### **13.4. Reporting Adverse Events**

All AEs and special reporting situations, whether serious or non-serious, will be reported from the time a signed and dated informed consent form is obtained until completion of the patient's final safety follow-up visit. The Sponsor will evaluate any safety information that is spontaneously reported by an Investigator beyond the time frame specified in the protocol. Adverse events reported after dosing will be classed as treatment emergent AEs.

All AEs, regardless of seriousness, severity, or presumed relationship to trial therapy, must be recorded using medical terminology in the source document and the eCRF. Whenever possible, diagnoses should be given when signs and symptoms are due to a common aetiology (e.g., cough, runny nose, sneezing, sore throat, and head congestion should be reported as "upper respiratory infection"). Investigators must record in the source documents and the eCRF their opinion concerning the relationship of the AE to trial therapy. All measures required for AE management must be recorded in the source document and reported according to Sponsor instructions. The patient must be provided, on the first day of trial medication (Day 1), with a "patient card" indicating the following:

- Patient number
- Name of the investigational product
- Investigator's name and 24-hour contact information
- Statement that the patient is participating in a clinical trial

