#### **13.4.1. Reporting Serious Adverse Events**

All SAEs occurring during clinical studies must be reported to the appropriate Sponsor designee (contract research organisation) immediately without undue delay of the investigator becoming aware of the event.

SAEs will be reported from the time a signed and dated informed consent form is obtained until completion of the patient's final safety follow-up visit.

However, the investigator must immediately notify the sponsor if, after completion of the clinical trial, he/she becomes aware of a serious adverse event in a subject suspected of being causally related to the investigational product.

Study Number: INVEX-CLIN-IIH-301 Protocol	Compound No.: Presendin
	Version: 5.0 for EU countries dated 08Dec2022

Information regarding SAEs will be transmitted to the Sponsor’s safety contact using the SAE Form, which must be completed and signed by the Investigator, and transmitted to the Sponsor’s safety contact immediately without undue delay.

The contact details are:

The Sponsor assumes responsibility for appropriate reporting of SAEs or SUSARs to the regulatory authorities. The Investigator (or Sponsor where required) must report these events to the appropriate Independent Ethics Committee (IEC) that approved the protocol unless otherwise required and documented by the IEC.

An annual safety report will be submitted to the Institutional Review Board once a year via the Investigator.

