#### 14.3.4.1. Adverse Events

All AEs, TEAEs, and SAEs will be coded using the MedDRA dictionary (the most recent version before starting the trial will be used).

An AE is defined as treatment-emergent if the first onset or worsening is after the first administration of trial medication.

The number and percentage of patients reporting TEAEs, grouped by MedDRA system organ class and preferred term will be tabulated by treatment group. Summaries will be presented for all TEAEs, TEAEs by severity and TEAEs by relationship to trial medication.

In the AE data listings, all AEs will be displayed. Adverse events that are not treatment-emergent will be flagged. The observation period in which an AE started will also be provided.

Non-protocol LPs, interventions for IIH, hospital admission for IIH exacerbation will be displayed by trial arm. Treatment failures will be displayed by trial arm.

Study Number: INVEX-CLIN-IIH-301 Protocol	Compound No.: Presendin
	Version: 5.0 for EU countries dated 08Dec2022

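### Sections 13.1.3 and 13.1.5 give opposite rules on whether a hospital admission for worsening IIH is reported as an SAE

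*Protocol*

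**What the plan says.** Section 13.1.3 of the protocol (version 5.0) defines an SAE. Among its general criteria is an event that "Requires inpatient hospitalization or prolongation of existing hospitalization". It adds a sentence specific to the disease under study: "Deterioration of IIH necessitating hospital admission will be recorded as an SAE and reported". It then gives two pre-defined exclusions: "Hospitalisation for unrelated elective procedures" and headache after lumbar puncture. Worsening IIH is not among them.

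Section 13.1.5, on expected adverse events, says: "Perceived deterioration of IIH necessitating attendance or admission to hospital will not be reported as an SAE". The sentence goes on: "but these events will be reported and recorded at follow-up".

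Three other places bear on what happens to such an event:

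- Section 13.4.1 requires SAEs to reach the sponsor's designee "immediately without undue delay of the investigator becoming aware of the event".
- Section 13.4 says: "All AEs, regardless of seriousness, severity, or presumed relationship to trial therapy, must be recorded".
- Section 14.3.4.1 (Adverse Events) says: "Non-protocol LPs, interventions for IIH, hospital admission for IIH exacerbation will be displayed by trial arm".

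Section 3.3 lists SAEs as a safety endpoint.

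**The concern.** Admission for worsening of the disease under study is an event that this trial should classify in one way only. With two opposite instructions in the same chapter, a site that works from 13.1.3 files an SAE form at once. A site that works from 13.1.5 notes the event at follow-up.

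Two things are at stake. The first is speed of reporting. Section 13.1.6 names no adverse events of special interest, so an admission that is not called an SAE has no other fast route to the sponsor. The second is the SAE table, because the count in a named safety endpoint would partly reflect which paragraph each site had read.

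**Working it through.** The protocol states no figure on this point that could be reproduced, so the check compares the texts.

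**1. Same event, two rules.** Take a patient admitted because IIH has worsened.

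| Question | Section 13.1.3 | Section 13.1.5 |
|---|---|---|
| Is the admission an SAE? | Yes, by the general hospitalisation criterion and by the IIH sentence | Not reported as one |
| When is it reported? | At once, through 13.4.1 | At follow-up |
| Does it count in the SAE endpoint of 3.3? | Yes | No |
| Is it recorded as an AE (13.4)? | Yes | Yes |
| Is it displayed by arm (14.3.4.1)? | Yes | Yes |

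The first three rows differ and the last two do not.

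**2. Can 'perceived' reconcile them?** It is the only qualifier that distinguishes 13.1.5. The protocol does not define it, does not say who judges it, and does not use it to separate two kinds of event. Suppose it means unconfirmed. An inpatient stay still meets the general criterion of 13.1.3 whether or not the deterioration is later confirmed. The reporting duty in 13.4.1 also starts when the investigator learns of the event, which may be before confirmation is possible.

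**3. Is there an exclusion that would give way to 13.1.5?** No. The exclusion list in 13.1.3 has two items, and neither covers IIH.

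**4. Is it a leftover of an amendment?** No. Both sentences stand in the current version 5.0. The appended version 4.0 has the same pair, in its sections 12.2 and 12.2.2.

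**5. Scale, under an assumption.** The inputs are 240 randomised patients (section 14.2.1) and the 5-10% expected to need more aggressive intervention (section 1.1, Visual Function). Assume that the admission rate for IIH deterioration is close to that percentage:

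- 0.05 × 240 = 12
- 0.10 × 240 = 24

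On this assumption up to 12 to 24 patients could be classified either way. The 5-10% counts interventions, not admissions. Some of those patients would have surgery that 13.1.3 separately names as an SAE (shunting, sheath fenestration or sinus stenting), although 13.1.5 does not exempt such cases from its own rule when they involve an admission.

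**The case against.** The strongest reply is that little is lost. Under 13.1.5 the event is still reported at follow-up, 13.4 has every AE recorded whatever its seriousness, and admissions for IIH are displayed by arm under 14.3.4.1. The document also leans one way: 13.1.3 has both a general criterion and a specific sentence, and leaves IIH off its exclusions. All of this stands, and it limits the consequence to SAE classification and prompt reporting. It does not tell a site which instruction to obey.

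Three stronger readings are tempting, and the documents do not support them.

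- *That these admissions go unreported.* They do not; they may go unreported as SAEs. Nor is it shown that the data safety monitoring committee would miss them. Section 15.7 gives it safety data for review and leaves the details to a charter that is not at hand.
- *That the SAE comparison between arms cannot be interpreted.* Sites are blinded (section 4.1.2), so a site's choice of section is made without knowledge of the arm. The likely result is a noisy or low SAE count, with no evident mechanism for bias between arms. Section 14.3.1.1.1 expects more use of ICP-lowering drugs on placebo, but the protocol says nothing about admissions by arm.
- *That the affected events are a large share of all SAEs.* The protocol gives neither an IIH admission rate nor an SAE rate. Its prediction that 6.7% of placebo patients will need rescue (section 4.1.1; 0.067 × 120 ≈ 8 patients) counts treatment failures. Section 10.2 allows rescue by medication and does not require admission. Rescue without admission or another seriousness criterion is an SAE under neither rule.

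**Conclusion.** The contradiction is real, stands in the current text, and cannot be resolved from the protocol itself. Its effect is specific: for an admission due to worsening IIH, both immediate SAE reporting and inclusion in the SAE endpoint depend on the section that a site follows. Recording as an AE, reporting at follow-up and display by arm are unaffected, and nothing in the primary endpoint, estimand or sample size is touched.

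The defect is textual and needs no number. The range of 12 to 24 of 240 patients shows possible scale only. It rests on the assumption that admissions approach the 5-10% expected to need more aggressive intervention.

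**What to change.** Reconcile sections 13.1.3 and 13.1.5 so that one rule applies. The simplest edit is to delete the reference to admission from 13.1.5. Any inpatient admission for worsening IIH then follows the hospitalisation criterion and the exclusion list that 13.1.3 already contains. Define 'perceived' or remove it. Limit 13.1.5 to hospital attendances that do not lead to admission and meet no other seriousness criterion.

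The by-arm display of IIH admissions in 14.3.4.1 is already planned and needs no change.

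The cost is a short edit to 13.1.5 in a protocol amendment, a memo to sites, and perhaps a few more SAE forms.

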#### **13.1.6. Adverse Events of Special Interest**

There are no Adverse Events of Special Interest (AESIs).

Study Number: INVEX-CLIN-IIH-301 Protocol	Compound No.: Presendin
	Version: 5.0 for EU countries dated 08Dec2022

### 13.2. Causal Relationship

Causal relationship assessment to drug treatments is required for purposes of reporting AEs. To promote consistency, the following guidelines should be taken into consideration along with good clinical and scientific judgment when determining the relationship of drug treatments to an AE:

- Probable relationship: event occurs in a plausible time relationship to the medication administration and cannot be explained by concurrent disease or other drugs or chemicals; the response to the withdrawal of the drug should be clinically plausible
- Possible relationship/ relationship cannot be ruled out: event occurs with a reasonable time sequence to the medication administration, but could also be explained by concurrent disease or other drugs or chemicals; information on the drug withdrawal may be lacking or unclear
- Unlikely relationship: event occurs with little temporal relationship to the medication administration and other factors such as drugs, chemicals or underlying disease provide plausible explanations
- Not related: event has no temporal relationship to the medication administration or there is a definite alternative aetiology

### 13.3. Severity Criteria

An assessment of severity grade will be made using the following categorical descriptors:

- Grade 1 means a relatively minor side effect
- Grade 2 means a moderate side-effect
- Grade 3 means a severe or medically significant but not immediately life-threatening side-effect
- Grade 4 means life-threatening consequences
- Grade 5 death related to AE

The exact definition of each number in the scale depends on the particular side effect according to Common Terminology Criteria for Adverse Events (CTCAE) v5.0 [[CTCAE](#)].

The Investigator should use clinical judgment in assessing the severity of events not directly experienced by the patient (e.g., laboratory abnormalities).

Study Number: INVEX-CLIN-IIH-301 Protocol	Compound No.: Presendin
	Version: 5.0 for EU countries dated 08Dec2022

Adverse events occurring as a result of LP should be specifically recorded. Occurrence of post lumbar headache will be specifically reported.

### **13.4. Reporting Adverse Events**

All AEs and special reporting situations, whether serious or non-serious, will be reported from the time a signed and dated informed consent form is obtained until completion of the patient's final safety follow-up visit. The Sponsor will evaluate any safety information that is spontaneously reported by an Investigator beyond the time frame specified in the protocol. Adverse events reported after dosing will be classed as treatment emergent AEs.

All AEs, regardless of seriousness, severity, or presumed relationship to trial therapy, must be recorded using medical terminology in the source document and the eCRF. Whenever possible, diagnoses should be given when signs and symptoms are due to a common aetiology (e.g., cough, runny nose, sneezing, sore throat, and head congestion should be reported as "upper respiratory infection"). Investigators must record in the source documents and the eCRF their opinion concerning the relationship of the AE to trial therapy. All measures required for AE management must be recorded in the source document and reported according to Sponsor instructions. The patient must be provided, on the first day of trial medication (Day 1), with a "patient card" indicating the following:

- Patient number
- Name of the investigational product
- Investigator's name and 24-hour contact information
- Statement that the patient is participating in a clinical trial

#### **13.4.1. Reporting Serious Adverse Events**

All SAEs occurring during clinical studies must be reported to the appropriate Sponsor designee (contract research organisation) immediately without undue delay of the investigator becoming aware of the event.

SAEs will be reported from the time a signed and dated informed consent form is obtained until completion of the patient's final safety follow-up visit.

However, the investigator must immediately notify the sponsor if, after completion of the clinical trial, he/she becomes aware of a serious adverse event in a subject suspected of being causally related to the investigational product.

Study Number: INVEX-CLIN-IIH-301 Protocol	Compound No.: Presendin
	Version: 5.0 for EU countries dated 08Dec2022

Information regarding SAEs will be transmitted to the Sponsor’s safety contact using the SAE Form, which must be completed and signed by the Investigator, and transmitted to the Sponsor’s safety contact immediately without undue delay.

The contact details are:

The Sponsor assumes responsibility for appropriate reporting of SAEs or SUSARs to the regulatory authorities. The Investigator (or Sponsor where required) must report these events to the appropriate Independent Ethics Committee (IEC) that approved the protocol unless otherwise required and documented by the IEC.

An annual safety report will be submitted to the Institutional Review Board once a year via the Investigator.

### **13.5. Reporting and Handling of Pregnancies**

Pregnant patients will be withdrawn from the trial.

Female patients will be instructed to notify the Investigator immediately if they become pregnant during the trial and up to 12 weeks after discontinuation/completion of trial medication. Pregnant patients will be withdrawn from further trial treatment. The patients will also be instructed to report pregnancies discovered after the last visit, if they believe that conception occurred during their participation in the trial.

A pregnancy as such is not an AE, unless there is a possibility that the trial medication has interfered with the efficiency of any contraceptive measures. The Investigator should report all pregnancies to the Sponsor contact or designee within 24 hours of being informed of them. The pregnancy report form should be used instead of the SAE form.

The pregnant patients will be followed until the end of the pregnancy. Any complication during the pregnancy should preferably be reported as an AE. The outcome of the pregnancy must be reported on the pregnancy report form. Any spontaneous abortion, stillbirth, birth defect/congenital anomaly, death, or other serious infant condition must be reported and followed up as an SAE.

Patients will give consent on enrolment that the Investigator will report any pregnancy to the Sponsor and that further information will be collected until delivery.

Study Number: INVEX-CLIN-IIH-301 Protocol	Compound No.: Presendin
	Version: 5.0 for EU countries dated 08Dec2022

## 14. DATA ANALYSIS AND STATISTICAL CONSIDERATIONS

The Statistical Analysis Plan (SAP) will be finalised prior to database lock providing detailed methods for the analyses outlined below.

### 14.1. Hypotheses

This trial compares outcomes in IIH patients under Presendin and matched placebo. The primary hypothesis that will be tested is:

- The ICP measurement in the Presendin group is equal to the ICP measurement in the placebo group at Week 24; against the alternative that the outcomes differ

### 14.2. Trial Design Considerations

#### 14.2.1. Sample Size Assumptions

The target sample size for the trial is 240 randomised patients, i.e., 120 patients per arm. We justify this figure in the following sections. The two outcomes for which we sought to power the study are ICP and PMD.

##### 14.2.1.1. Intracranial Pressure Power

The most difficult parameters to specify for a sample size calculation pertain to the variability of outcomes. We present a brief summary of the literature. Baseline standard deviations (SD) of ICP in previous trials were: 5.4 (n=10) and 6.3 (n=17) in the Drug Trial [Markey, 2017]; 5.0 (n=16) (data on file); and 5.7 (n=32) and 5.3 (n=30) in the Weight Trial [Ottridge, 2017]. Post-baseline standard deviations were slightly lower (and less than 6.0) in three of these five arms; and increased slightly in one (but remained less than 6.0). The post-baseline standard deviation however increased to over 8.0 in the surgery arm of the Weight Trial because the surgical intervention dramatically impacted ICP in some patients. In the NORDIC trial [Wall, 2014] however, the standard deviation of baseline ICP was much higher, at 9.4 in the treatment arm (n=86). Seeking to avoid underpowering the study, we elected to proceed with the SD estimate for the NORDIC trial as this is the most similar trial population to the planned IIH EVOLVE trial (both recruiting acute IIH). We assume that control arm baseline and 24-week ICP SD equals 9.4, Presendin baseline ICP SD equals 9.4, and Presendin 24-week ICP SD equals 10.4. These values assume the variability of ICP measures in untreated patients is as high as has been seen in the NORDIC trial and assumes that the variability in treated patients is slightly higher still. We anticipate that the standard deviation will be slightly higher in the experimental arm as treatment effects will potentially manifest changes in ICP. However, we do not expect such variability to be as inflated in this trial relative to control as it was

Study Number: INVEX-CLIN-IIH-301 Protocol	Compound No.: Presendin
	Version: 5.0 for EU countries dated 08Dec2022

in the Weight Trial because of the likely difference in treatment effect between surgical and drug interventions.

Under this parameterisation, when testing for a difference between arms at 24-weeks of 5 CSF (justified below) using a total sample size of 240, assuming that up to 50% of observations are missing (i.e. 60 final LPs are completed in each arm), using a 5% significance level by Analysis of Covariance (ANCOVA) adjusted for baseline ICP, the two stratification variables, and treatment arm, we expect to have approximately 85% power. If 40% of observations are missing (i.e. 72 final LPs are completed in each arm), we expect power to be 91%. These figures have been inferred by computer simulation. Of the 165 patients in IIHTT [Wall, 2014] it was reported that “only 85 participants (47 [55%] in the [treated] group and 38 [48%] in the placebo group) agreed to a lumbar puncture at month 6.”

We expect a high rate of missing data because lumbar puncture is an invasive procedure that patients can find painful and traumatising [Scotton, 2018]. If patients have an unpleasant experience at the diagnostic LP they are also more likely to decline the LP at trial outcome. If patients do decline the final LP, logically it will be because of the baseline experience rather than their prevailing ICP. If data for the LP at 24 weeks is missing, the reason will be recorded.

Outcomes from previous trials show that baseline and post-baseline distributions of ICP show central tendency with approximate symmetry, so we conclude that normality is a reasonable assumption and therefore ANCOVA is a defensible analysis method.

